9.5.3 Analysis of Efficacy Variables

All efficacy analyses will be conducted on both the ITD and PP populations. The ITD population will be the primary analysis set.

9.5.3.1 Primary Endpoint Arm 1

The distribution of TUV_{joint} in HC subjects will be summarized with descriptive statistics: mean, standard deviation, n, minimum, maximum, and median per reader, joint, and view. The 5 and 95 percentiles will be estimated with quantile regression fitting an intercept as a fixed term. The lower and upper limits of normal TUV_{joint} will be determined using non-parametric confidence intervals and kernel density-based confidence intervals.

9.5.3.2 Primary Endpoint Arm 2

Localization of tilmanocept in the hands and wrists will be summarized with frequency counts and percentages by reader and joint.

9.5.3.3 Secondary Endpoint Arm 1

Normal quantile plots will be provided per joint and reader, along with the *p*-value for the Shapiro-Wilk test of Normality.

9.5.3.4 Secondary Endpoints Arm 2

SUV will be calculated and summarized on both a per-joint and a total of all joints with summary statistics: mean, standard deviation, n, minimum, maximum, and median.

The predictive value of planar scans for SPECT/CT qualitative findings will be summarized per joint and reader with a crosstabulation and the uncertainty coefficients for row | column, column | row, and symmetric. The planar result will be deemed "positive" (i.e., inflamed) if $TUV_{joint} > 95$ percentile of the reader results for the same joint in Arm 1. Otherwise, the planar result will be deemed "negative".

Additional efficacy analyses may be described in the NAV3-35 Statistical Analysis Plan (SAP).

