# **List of Abbreviations and Definitions of Terms**

Term	Definition
Δ	Greek letter delta, used to represent the change in a
	particular variable
μg	microgram
ACPA	anti-citrullinated protein/peptide antibody
ACR/EULAR	American College of Rheumatology/ European League
	Against Rheumatism
AE	adverse event
Anti-TNF-α	Anti-Tumor Necrosis Factor $\alpha$ biological Disease Modifying
bDMARD	Anti-Rheumatic Drug
CDAI	Clinical Disease Activity Index
CFB	change from baseline
CI	confidence interval
CRF	case report form
CSR	clinical study report
CT	X-ray computed tomography
CV	coefficient of variation
DAS28	Disease activity score used with the ACR/EULAR 2010 RA
	guidelines
ECG	electrocardiogram
FDA	Food and Drug Administration
HAQ-DI	Health Assessment Questionnaire Disability Index
HC(s)	healthy control(s)
ICH	International Conference on Harmonization
ITD	intent-to-diagnose
IV	intravenous
mCi	milliCurie (37x10  becquerels; 37megabecquerels)
MCP	metacarpophalange
MedDRA	Medical Dictionary for Regulatory Activities
NPV	Negative Predictive Value
OA	Osteoarthritis or Overall Accuracy, depending on context
PIP	proximal interphalange
PP	per protocol
PPV	Positive Predictive Value
RA	rheumatoid arthritis
ROI	region of interest
RR	reference region
SAE	serious adverse event
SAP	statistical analysis plan
SOC	system organ class
SPECT	single photon emission computed tomography

Term	Definition
Tc 99m	technetium-99m metastable isotope; γ-emitting (half-life
	6.02 h)
TEAE	treatment-emergent adverse event
TESAE	treatment-emergent serious adverse event
tilmanocept	DTPA Mannosyl Dextran (the US Adopted Name for the
	drug substance of Lymphoseek)
TUV	Tilmanocept uptake value
US	United States
$\bar{X}_{BRAIN}$	the decay-corrected average voxel intensity of the brain
	RR of a subject at the anterior view at 1 or 3-hours post-
	injection
$\bar{X}_{ROI}$	the decay-corrected average voxel intensity of a region of
	interest

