#### Arm 2:

- Quantitative evaluations of Tc 99m tilmanocept localization from SPECT/CT within synovial spaces of the bilateral hands and wrists in HCs and RA subjects.
- Normative joint-specific standardized uptake value (SUV).
- Predictive value of planar scans for SPECT/CT scans.

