#### Arm 2:

SUV will be calculated and summarized on both a per-joint and a total of all joints with summary statistics: mean, standard deviation, n, minimum, maximum, and median. The formula for SUV is:

$$SUV = \frac{r}{(a'/w)};$$

where:

r: The radioactivity activity concentration [kBq/mL]

a': The decay-corrected amount of injected radiolabeled FDG [kBq]

w: The weight of the patient [g]

The predictive value of planar scans for SPECT/CT qualitative findings will be summarized per joint and reader with a crosstabulation and the uncertainty coefficients for row | column, column | row, and symmetric. The planar result will be deemed "positive" (i.e., inflamed) if TUVjoint > 95 percentile of the reader.

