#### Localized on SPECT/CT

Joint	Reader	No	Yes	Total
xxxxxxxxxxx	xx	xxx	xxx	XXX
		XX.X%	xx.x%	
	xx	xxx	xxx	XXX
		XX.X%	xx.x%	
	xx	xxx	xxx	XXX
		xx.x%	XX.X%	

STATKING Clinical Services (DD-MMM-YYYY) Source Program: xxxxxxx.sas

Table format is repeated for the PP population.

Page x of y

Table 15. Shapiro-Wilk P-Value for Normality Test for TUVjoint Data - All Arm 1 and 2 Healthy Control Subjects

Navidea Biopharmaceuticals - Study No. NAV3-35

ITD Population (N=xxx)

Test for Normality

Test	Statistic	P-Value
Shapiro-Wilk	xxx	xxx

STATKING Clinical Services (DD-MMM-YYYY) Source Program: xxxxxxx.sas

All Table format is repeated for the PP population

Page x of y

Table 17. Predictive Value of Planar Scans for SPECT/CT Per Joint and Reader
Navidea Biopharmaceuticals - Study No. NAV3-35

ITD Population (N=xxx)

SPECT/CT (Standard of Truth)

Reader	Joint	Planar Scans	Positive	Negative	Total	Uncertainty Coefficients	Estimated 95 %tile
XX	XXX	TUVjoint > 95 (Positive)	XXX	XXX	XXX	XXX	XXX
		Negative	XXX	XXX	XXX		
		Total	XXX	xxx	XXX		
	XXX	TUVjoint > 95 (Positive)	XXX	xxx	xxx	xxx	XXX
		Negative	XXX	XXX	xxx		
		Total	XXX	XXX	XXX		
xx	xxx	TUVjoint > 95 (Positive)	xxx	XXX	xxx	xxx	xxx
		Negative	XXX	XXX	XXX		
		Total	XXX	XXX	XXX		
	xxx	TUVjoint > 95 (Positive)	xxx	XXX	XXX	XXX	XXX
		Negative	XXX	XXX	XXX		
		Total	XXX	xxx	XXX		
XX	XXX	TUVjoint > 95 (Positive)	XXX	xxx	xxx	xxx	xxx
		Negative	XXX	XXX	XXX	*****	*****
		Total	XXX	XXX	XXX		
	xxx	TUVjoint > 95 (Positive)	xxx	xxx	xxx	xxx	xxx
		Negative	XXX	XXX	XXX		
		Total	XXX	XXX	XXX		

If there are no major protocol deviations, then analysis tables for the ITD and PP populations will contain identical results. STATKING Clinical Services (DD-MMM-YYYY)
Source Program: xxxxxxx.sas

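### Predictive value of planar scans for SPECT/CT is summarised by uncertainty coefficients that ignore direction; the counts are shown, but no PPV, NPV or confidence interval is planned

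*SAP*

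**What the plan says.** SAP section 4.1.2 lists, as an Arm 2 secondary endpoint, "Predictive value of planar scans for SPECT/CT scans". SAP section 4.2.2 reports it for each joint and reader as a crosstabulation together with "uncertainty coefficients for row | column, column | row, and symmetric". Protocol section 9.5.3.4 plans the same summary. A joint is planar-positive when its TUV lies above the 95th percentile; the protocol ties this to the same reader and joint in Arm 1.

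The Table 17 shell in SAP Appendix B prints the four cell counts and totals for each reader and joint. Its columns are headed "SPECT/CT (Standard of Truth"). Beside the counts are one column called "Uncertainty Coefficients" and one for the estimated 95th percentile. The SAP abbreviation list includes "Positive Predictive Value", its negative counterpart and overall accuracy, but no analysis section or table shell uses them. No confidence interval is planned for this endpoint, and nothing says what to show when a row or column of the table is empty.

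Arm 2 has 5 HC and 10 RA subjects. There are 22 joints and three readers, and SAP section 2.5 rules out aggregating over readers.

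**The concern.** The endpoint asks how well a planar call predicts the SPECT/CT call, and the shell treats SPECT/CT as the reference. The usual answers are PPV, NPV, sensitivity and specificity, each with an interval. The planned summary statistic is instead an entropy-based association measure, which takes the same value whether planar agrees with SPECT/CT or contradicts it. Read without its table, a coefficient cannot be interpreted as predictive value. With at most 15 subjects behind each table, the planned output would also give no indication of how imprecise any derived PPV or NPV is.

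**Working it through.** The documents give no target, power or precision for this endpoint, and the Arm 2 size rests on the sponsor's business purposes, so there is no stated figure to reproduce.

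**Definitions.** Let R be planar (rows: positive, negative), C be SPECT/CT (columns: positive, negative) and H be entropy. Then I = H(R) + H(C) − H(R,C), U(C|R) = I/H(C), U(R|C) = I/H(R), and symmetric U = 2I/(H(R) + H(C)).

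**Direction.** These are illustrative tables with n = 15, the most that Arm 2 can supply per joint and reader if left and right are separate.

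| Table | PPV | NPV | U(C\|R) | U(R\|C) | Symmetric |
|---|---|---|---|---|---|
| [[3, 1], [2, 9]] | 3/4 = 75% | 9/11 = 82% | 0.218 | 0.239 | 0.228 |
| [[1, 3], [9, 2]] (columns swapped) | 1/4 = 25% | 2/11 = 18% | 0.218 | 0.239 | 0.228 |
| [[5, 0], [0, 10]] (perfect) | 100% | 100% | 1 | 1 | 1 |
| [[0, 10], [5, 0]] (perfectly reversed) | 0% | 0% | 1 | 1 | 1 |

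For the first two tables, in natural logs, H(R) = 0.580, H(C) = 0.637 and H(R,C) = 1.078. Hence I = 0.139 and symmetric U = 2 × 0.139/(0.580 + 0.637) = 0.228. Swapping the columns changes none of these entropies.

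**Precision.** In the first table the exact (Clopper-Pearson) 95% CI is 19% to 99% for PPV 3/4 and 48% to 98% for NPV 9/11.

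**Empty margins.**
- No SPECT/CT positives, for example [[0, 5], [0, 10]]: H(C) = 0, so U(C|R) is 0/0, while U(R|C) and symmetric U are 0.
- No planar positives, for example [[0, 0], [3, 12]]: H(R) = 0, so U(R|C) is 0/0, while U(C|R) and symmetric U are 0.
- Neither has positives, [[0, 0], [0, 15]]: all three are 0/0.

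**How often one given positive margin is empty.** The documents give no positivity rates, so these are assumptions: 5% per joint in HCs, a range in RA subjects, and independence. With sides separate (n = 15) the chance is 0.95^5 × (1 − p)^10, where p is the RA rate. With left and right pooled (n = 30) it is the square of that. The last column is the n = 15 chance times 66 (22 joints × 3 readers).

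| RA rate p | n = 15 | n = 30 | Expected of 66 tables, sides separate |
|---|---|---|---|
| 10% | 0.774 × 0.349 = 27% | 7% | 17.8 |
| 20% | 0.774 × 0.107 = 8% | 0.7% | 5.5 |
| 30% | 0.774 × 0.028 = 2% | under 0.1% | 1.4 |
| 50% | 0.1% | under 0.1% | under 0.1 |

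**The case against.** The strongest reply is that the same sentence plans a crosstabulation and Table 17 prints every cell. Direction is therefore visible, a reversed predictor would not pass unnoticed, and PPV, NPV and even exact intervals can be computed from the counts. That stands. The gap is what the output summarises, not lost data. It remains a gap, because readers would have to do this by hand over as many as 66 small tables. U(C|R) is also a recognised measure of how far planar reduces uncertainty about SPECT/CT, and this is a descriptive secondary endpoint in a small feasibility arm. Both points bear on severity. Neither supplies a predictive value.

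A reader might infer that many of the tables would have no defined coefficient at all. The documents do not support this. All three coefficients are planned, and a single empty margin removes only one of them. The frequency rests on assumed rates and on keeping left and right separate, which is unsettled for Table 17: the endpoint speaks of bilateral joints and the by-age figures list 11 joint types, while Figures 3 and 5 split by hand. Nor are undefined values an argument for the alternatives: sensitivity is 0/0 with no SPECT/CT positives, and PPV is 0/0 with no planar positives.

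A reader might also take the abbreviation list as evidence that PPV and NPV were planned and then dropped. The list carries other terms that the analyses do not use, such as HAQ-DI and CDAI, so it shows only that the terms are unused.

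**Conclusion.** The point holds in a limited form. The planned coefficients cannot separate a correct from a reversed predictor (0.228 both ways in the example, 1 for both perfect and perfectly reversed tables). They sit beside a crosstabulation that can, but no predictive value or interval is planned for an endpoint named predictive value. The direction result is algebraic and needs no assumption. The interval widths assume at most 15 subjects per joint and reader.

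The empty-margin issue is secondary. One coefficient becomes 0/0 and the other two become 0, and a forced 0 looks the same as a 0 from genuine lack of association. Under the assumed 5% HC rate and RA rates of 10% to 30%, a given positive margin is empty in about 27% to 2% of tables with sides separate, and in about 7% to under 0.1% with sides pooled. This calls for a display rule. It is not a reason to say that the analysis fails. The change is worthwhile and cheap, and no data are at risk.

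**What to change.** In SAP section 4.2.2 and the Table 17 shell:

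- Keep the crosstabulation and add PPV, NPV, sensitivity, specificity and overall accuracy with exact 95% CIs, per joint and reader.
- State whether left and right are separate. Exact binomial intervals suit one joint per subject; if sides are pooled, the interval must allow for two joints from the same person.
- Add one estimate per reader, pooled over joints, with clustering by subject (for example a bootstrap that resamples whole subjects). This respects the rule against combining readers. With 15 subjects it will be approximate.
- Print not estimable wherever a denominator is 0, for the new measures and the coefficients alike.
- Keep the uncertainty coefficients as supplementary and label each of the three; the shell has one column for them.
- Add a footnote that PPV and NPV reflect the 10:5 mix of RA and HC subjects and do not carry over to another prevalence.

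The cost is SAP wording, a shell revision and minor programming, with no new data. The downside is that many very wide intervals will be on display, which is an accurate picture of what Arm 2 can show joint by joint.

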# 5.0 Analysis of Safety

#### 5.1 Description of Safety Variables

The safety analysis variables are defined as follows:

- Adverse Events (AEs)
- Clinical Laboratory Tests (hematology, serum chemistry, urinalysis, RA panel)
- Vital Signs

#### 5.2 Description of Safety Analysis

The following describes the safety analyses to be performed for the study. All safety analyses will be performed on the safety population. Follow up timing will vary by arm as noted above.

#### **Adverse Events**

Adverse events will be observed for each subject from signing of informed consent until termination from the study. AEs will be coded using the Medical Dictionary for Regulatory Activities (MedDRA®). A treatment-emergent AE (TEAE) is defined as an AE whose start date is on or after the initial procedure date. Based on the coded terms, frequencies of each TEAE will be summarized by MedDRA® preferred term within system organ class (SOC), by severity grade, and by relationship to Tc 99m Tilmanocept for each arm and overall.

A summary of TEAEs will be constructed showing the following by arm and overall:

- Number of subjects with at least one TEAE
- TEAEs by arm and severity grade
- TEAE by arm and relationship to Tc 99m tilmanocept
- TEAEs by arm and relationship of TEAE to study procedure
- Number of subjects with at least one treatment emergent serious adverse event

Treatment-emergent serious adverse events (TESAEs) will be tabulated by MedDRA® preferred term within SOC by arm and overall.

A by-patient AE data listing of all AEs including verbatim term, coded term, grade, and relation to study drug will be provided.

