7.1 Schedule of Evaluations

7.1.1 Arm 1

Visit 1 (Screening; Day -30 to Day -1)

- Preliminary review of inclusion and exclusion criteria
- Obtain signed informed consent for study participation
- Allocation of unique subject number; this number will be used to document the subject data in the case report forms (CRFs) and enrollment log
- Demography date of birth, gender, race, ethnicity
- Medical surgical history all relevant prior medical and surgical conditions will be recorded in the CRF. Documented medical conditions will also note the month and year of onset if the condition is still active.
- Concomitant medications (within 30 days before injection).
- Vital signs (body temperature, heart rate, blood pressure, and respiratory rate after at least 1 minute in a resting position)
- Physical examination will include an assessment of height, weight, and examination of general appearance, skin, eyes, ears, nose, throat, head and neck (including thyroid), lungs, heart, abdomen, lymph nodes, musculoskeletal, and nervous system. Any clinically relevant finding is to be documented as a baseline finding. Physical exams that are conducted as standard of care prior to signing informed consent may be used if they are performed within 30 days of injection.
- Clinical laboratory tests study subjects will have blood obtained for hematology, chemistry, and an RA panel (see Table 7)
- Urine collection for routine analysis
- Urine pregnancy test for women of child-bearing potential. Females of child bearing potential are defined as women that are not surgically sterile (hysterectomy or bilateral oophorectomy) nor postmenopausal for at least 1 year prior to screening. Women who are not of childbearing potential will not require a pregnancy test.
- 2010 ACR/EULAR: to confirm that the subject is clinically free of inflammatory disease and joint pain Swollen and tender joints will be identified and documented during physical examination as established by the 2010 ACR/EULAR.

Visit 2 (Tc 99m Tilmanocept Administration and Imaging; Day 0)

All subjects will be assessed for adverse events in an ongoing manner from the day of injection through the end of participation.

Pre-Tc 99m Tilmanocept Administration

The following procedures will be completed for all subjects on the day of injection prior to the administration of Tc 99m tilmanocept:

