IV administration of Tc 99m tilmanocept will be at study time 00:00. The preferred site of IV placement will be the left or right antecubital vein. The filled syringe will be connected to the catheter for a slow push injection (30-60 seconds). At the completion of the injection, a 10-mL sterile normal saline flush will be administered. The IV administration will be performed in the nuclear medicine department by an onsite Certified Nuclear Medicine Technologist or Nuclear Medicine Physician. Subjects will be continuously monitored for adverse events.

0 to 30 Minutes Post-Tc 99m Tilmanocept Administration

- Assessment of adverse events
- Vital signs after at least 1 minute in a resting position (body temperature, heart rate, blood pressure, and respiratory rate)

60 - 75 Minutes Post-Tc 99m Tilmanocept Administration

- Assessment of adverse events
- Image acquisition (in the following order):
 - 1. Planar scan of the bilateral hands and wrists acquired per NAV3-35 Image Acquisition Guidelines followed by preparation (up to 10 minutes) for the subsequent scan;
 - 2. SPECT/CT of the bilateral hands and wrists acquired per NAV3-35 Image Acquisition Guidelines

Visit 3 (Day 5 ± 3; Follow-up Telephone Safety Assessment)

- Review of concomitant medications
- Assessment of adverse events

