8.5 Adverse Events

8.5.1 Definition of Adverse Event

The definitions below follow International Conference on Harmonization (ICH) – Good Clinical Practice (GCP) (see also ICH Guideline for Clinical Safety Data Management: Definitions and Standards for Expedited Reporting).

An AE is defined as any untoward medical occurrence in a subject administered a pharmaceutical product and which does not necessarily have a causal relationship with this treatment. An AE can therefore be any unfavorable and unintended sign (including an abnormal laboratory finding), symptom, or disease temporally associated with the use of a medicinal (investigational) product, whether or not considered related to the medicinal (investigational) product.

Any clinically significant change in a condition (worsening) from screening that results in a change in subject management will be considered an AE and will be recorded on the AE page of the CRF.

By definition for this study, all untoward medical occurrences beginning on the Visit 2 (Day 0) until the final visit (variable per arm) are to be reported as AEs. AEs continuing after study completion will be followed to normalization or stabilization. Additionally, untoward medical events occurring prior to the day of Tc 99m tilmanocept administration will be collected and added to the subject's medical history unless they are related to a study procedure, in which case the event will be recorded as an AE. SAEs will be reported from the time of consent through the end of participation.

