9.5.4 Analysis of Safety Variables

All safety analyses will be conducted on the safety population.

All AEs will be observed for each subject from the time of signing of informed consent until study completion. A treatment-emergent AE (TEAE) is defined as an AE whose start date is on or after the initial procedure date. If the procedure date or the AE start date is missing, the AE will be considered treatment emergent.

Prior to analysis all AEs will be coded using the MedDRA coding dictionary. Based on the coded terms, TEAEs will summarized by cohort and overall as follows:

- By system organ class (SOC) and preferred term (PT);
- By SOC and PT and relation to the study drug;
- By SOC and PT and severity.

Observed and change from baseline vital sign parameters and hematology, clinical chemistry and urinalysis parameters will be summarized using descriptive statistics (mean, standard deviation, median, and range) for each Arm and overall at each time point.

Other safety analyses may be described in the SAP for the study.

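### Treatment-emergent AEs are anchored to an undefined initial procedure date, compared by date only, so some events that begin before the injection are counted as treatment-emergent

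*SAP*

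**What the plan says.** SAP 5.2 (Adverse Events) gives the rule: "A treatment-emergent AE (TEAE) is defined as an AE whose start date is on or after the initial procedure date". Protocol 9.5.4 repeats it and adds a rule that the SAP lacks: "If the procedure date or the AE start date is missing, the AE will be considered treatment emergent".

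The recording rules decide which events can reach that test:

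- **Observation window.** The SAP says: "Adverse events will be observed for each subject from signing of informed consent until termination from the study".
- **Before Day 0.** Under Protocol 8.5.1, events go to medical history "unless they are related to a study procedure, in which case the event will be recorded as an AE".
- **From Day 0.** Under Protocol 8.5.1, "all untoward medical occurrences beginning on the Visit 2 (Day 0) until the final visit (variable per arm) are to be reported as AEs". The boundary is the visit day, not the injection.
- **Serious events.** Under Protocol 8.5.1, "SAEs will be reported from the time of consent through the end of participation". Protocol 8.5.5 requires all SAEs to be entered on the AE eCRFs.

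On timing, Protocol 7.1 places screening at "Visit 1 (Screening; Day -30 to Day -1") and says "IV administration of Tc 99m tilmanocept will be at study time 00:00". An AE assessment is scheduled on Day 0 before that time.

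**The concern.** A treatment-emergent flag is meant to separate events that could follow exposure from events that could not. In this single-dose study the exposure has an exact start time, yet the flag is tied to something else, and that something is not defined. Two programmers could classify the same event differently and both could claim to follow the plan.

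Safety is a stated objective, and AE Tables 19 to 24, including the table of treatment-emergent serious events, rest on this flag. Protocol 8.5.4 reports no product-related AE or SAE in about 280 intravenous administrations, so counts should be low. Two of the three subject groups are very small, so a single misplaced event would show.

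**Working it through.** The plan states no figure to reproduce. The check applies the rule under each reading of *initial procedure date* and then does simple arithmetic on the visit windows and group sizes.

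**Reading A: the term means Day 0.** Protocol 4.2 refers to injection and imaging as Day 0 procedures, which supports this reading.

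1. From Day 0, every untoward occurrence is an AE by calendar day (Protocol 8.5.1 and 8.5.3).
2. AEs are assessed on Day 0 before injection (Protocol 7.1). Appendix 1 shows AE monitoring in the column from -00:30 to -00:01.
3. Injection is at 00:00.
4. An event that starts that morning before injection has start date = Day 0, so start date ≥ procedure date is true and the event is a TEAE.

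The events misclassified are those with onset on Day 0 before the injection.

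**Reading B: the term means the first study procedure.** SAP 1.2 calls the Visit 1 assessments screening procedures. SAP 5.2 also tabulates relationship to study procedure separately from relationship to the drug, so procedure there is not simply another word for injection.

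1. Procedure-related events from Day -30 to Day -1 are recorded as AEs (Protocol 8.5.1 and 8.5.3) and meet the date test.
2. SAEs from consent onward are entered on the AE eCRFs (Protocol 8.5.1 and 8.5.5). One starting on or after the first screening procedure meets the test and could enter Table 21.
3. Non-serious events before Day 0 that are not procedure-related go to medical history and cannot become TEAEs.

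The events misclassified are those of Reading A plus items 1 and 2.

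**Window length under Reading B.** Screening 30 days + Day 0 (1 day) + follow-up to Day 8 at the latest (5 + 3 = 8 days) = 39 days, which matches the maximum in Protocol 3.3. The share before the injection day is 30/39 = 77%. This is calendar time, not a share of events.

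**Weight of one misclassified subject at planned enrolment:**

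| Column | Planned n | One subject |
|---|---|---|
| RA (Arm 2) | 10 | 1/10 = 10% |
| Healthy controls (Arm 2) | 5 | 1/5 = 20% |
| Healthy controls (Arm 1) | 120 | 1/120 = 0.8% |
| Overall | 135 | 1/135 = 0.7% |

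The documents give no AE rate by study period, so the expected number of misclassified events cannot be calculated.

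**Are the data for a better rule available?** Yes. Protocol 8.5.3 requires date and time of onset for every AE. SAP Data Listing 11 has columns for AE start date and time, injection date and time, and the treatment-emergent flag.

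**Missing dates.** The protocol classifies an AE with a missing start date as treatment-emergent. The SAP omits this rule and, in 2.3, rules out imputation, so the SAP alone leaves such an event unclassified. Neither document covers a Day 0 event with a known date but no onset time.

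**The case against.** The strongest reply is that Reading A is the natural one. General AE reporting starts on Day 0, and Data Listing 11 puts the injection time beside the flag. If screening were the anchor, nearly every recorded AE would be treatment-emergent and the flag would do no work. On that reading the error is confined to the hours of Day 0 before injection and cannot hide a drug signal, because it only adds events. Relationship to drug and relationship to procedure are rated separately and shown in Tables 20, 23 and 24, so an event from a screening blood draw could still be shown as procedure-related and not drug-related. Data Listing 11 would expose any pre-injection onset. The AE analysis is descriptive, and no efficacy endpoint depends on it.

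Most of this stands and limits the size of the point. It does not remove it: the term is still undefined, and a date-only test misclassifies Day 0 pre-injection events even on the favourable reading.

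A reader might infer more than the documents support:

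- That 77% of the treatment-emergent window is before drug, so TEAE incidence is heavily inflated. The figure holds only under Reading B and describes days. Ordinary non-serious events on those days go to medical history, and the screening assessments in Protocol 7.1 give little scope for procedure-related AEs.
- That all safety tables are affected. Laboratory and vital-sign Tables 25 to 31 do not use the flag.
- That subjects never injected add events. The safety population contains injected subjects only.

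**Conclusion.** The point holds as a defect in a definition, with limited reach. Under either reading, some events with onset before exposure are counted as treatment-emergent: Day 0 pre-injection events at the least, and procedure-related AEs and SAEs from screening at the most. The effect is confined to AE Tables 19 to 24 and runs toward over-reporting. Its size in events is unknown. In proportions, one subject moves the RA column by 10% and the Arm 2 healthy-control column by 20%, but the Arm 1 and overall columns by less than 1%.

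These percentages assume the planned group sizes; the safety population may be larger if subjects are replaced after injection. Including screening SAEs of any cause under Reading B assumes that the eCRF instruction in Protocol 8.5.5 prevails over the medical-history rule in 8.5.1. The correction should be made before the safety tables are programmed, because it removes the ambiguity and needs no new data.

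**What to change.** Make the same change in SAP 5.2 and Protocol 9.5.4:

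1. Define a TEAE as an AE with onset date and time at or after the start of the Tc 99m tilmanocept injection, or an AE that worsens after it. Drop *initial procedure date*.
2. Count a Day 0 event with missing onset time, and any event with missing onset date, as treatment-emergent. This carries the protocol's missing-date rule into the SAP and extends it to missing times.
3. List AEs with onset before injection separately, with their relationship to study procedure, so that no recorded event is lost from the report.

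The cost is a few sentences in each document and one additional listing or a subset of Data Listing 11. No new data collection is needed.
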